7. PARTICIPANT IDENTIFICATION

7.1. Study Participants

Participants diagnosed with rectal cancer that is operable and patients who have already had rectal cancer removed by TEM surgery in Oxford since 2007.

7.2. Inclusion Criteria

- Participant is willing and able to give informed consent (in English) for participation in the study, or gave informed consent for donation of tissue for research at the time of surgery.
- Male or Female, aged 18 years or above.
- Diagnosed with operable rectal cancer.
- Due to undergo, or has already undergone, TEM surgery to remove rectal cancer.
- A useable tissue sample has already been, or will be, taken as part of routine surgery.

7.3. Exclusion Criteria

The participant may not enter the study if ANY of the following apply:

- Age less than 18
- Adults who are not able to give consent or who are deemed vulnerable.
- Participants who do not have a useable tissue sample will be excluded.

8. STUDY PROCEDURES

8.1. Recruitment

All patients who have undergone TEM surgery to remove a rectal cancer since 2007 are eligible, as well as new patients having surgery over the study period. Data on these patients is recorded as standard practice in the Oxford TEM database. There will be different groups, according to the time of surgery and whether or not potential participants consented for tissue donation, requiring different identification and recruitment strategies.

Already had surgery groups

Screening: A member of the care team will extract a list of patients who have had TEM surgery for rectal cancer since 2007 from the TEM database, identified by MRN (OUH medical records number) only. The care team member will then screen the casenotes for these patients to determine whether or not they consented to donation of tissue for research on the surgical consent form.

- Group A: Those who already consented for tissue donation

The majority of potential participants signed a donation of tissue for research statement at the time of surgery. If this statement has been agreed to, patients will be considered to have consented to participate in the study. The care team member will pass the list of MRNs (and linked anonymized data) for these patients to the researcher.

- Groups B & C: Those who did not consent to tissue donation at the time of surgery

Once these have been identified, the care team member will identify whether these patients are still undergoing follow-up at Oxford hospitals. For those who are undergoing follow-up (Group B) the member of the care team will provide the researcher with the MRN and date of the next follow-up appointment. For those who are no longer under follow-up (Group C), the member of the care team will post an information sheet and consent form to the potential participant.

For Group B the researcher will contact the patient during their follow-up visit and give them an information sheet about the study. They will be invited to sign a consent form if they wish to participate. Group C will receive an information sheet and consent form through the post, and will be provided with a telephone number should they wish to discuss the study further.

New patients who have not yet had surgery (Group D)

New patients, who have not yet had surgery, will be identified at colorectal cancer multi-disciplinary meetings. This will involve reviewing the clinical, histological and radiological investigations with other surgeons, oncologists, radiologists and pathologists as part of the normal clinical review process. Patients who are deemed suitable for TEM surgery will be considered eligible. Identified potential participants will then be approached by an investigator, who is a member of their direct care team, during their routine pre-operative clinic visit. They will be provided with an information sheet and given time to ask questions. Patients agreeing to participate will be recruited on their subsequent visit for surgery.

8.2. Screening and Eligibility Assessment

Not applicable. Participation will be sought from patients undergoing or who have undergone TEM surgery for rectal cancer.

The participant will be allowed as much time as wished to consider the information, and the opportunity to question the Investigator, their GP or other independent parties to decide whether they will participate in the study. Written Informed Consent will then be obtained by means of participant dated signature and dated signature of the person who presented and obtained the Informed Consent. The person who obtained the consent must be suitably qualified and experienced, and have been authorised to do so by the Chief/Principal Investigator. A copy of the signed Informed Consent will be given to the participant. The original signed form will be retained at the study site.

8.4. Study Visit

No specific visit is required. Consent will be taken when the patient attends for surgery, or for patients who have previously had surgery, consent will be taken during a routine follow-up visit or by post.

8.5. Data Handling

For Group A patients, who gave consent at the time of surgery, a member of the care team will extract the relevant data, including tumour characteristics, any (neo-)adjuvant treatment details and outcome information, identified only by MRN, from the TEM database. The care team member will then securely transfer this anonymised data, identifiable by MRN only, to the research team. The research team will then allocate each participant a study ID according to the recruitment log, and replace the MRN with the unique study ID. The transfer will be done using a password protected spreadsheet sent via encrypted email. For all other patients, who sign a specific study consent form, the researcher will prepare the data extract from the TEM database, identified only by MRN, and then replace the MRN with a study ID. The researcher will securely provide a list of MRNs, with date of surgery, to the pathology department. The MRNs will be linked to a unique study ID in a separate recruitment log.

8.6. Sample Handling

A list of MRN (medical record numbers) and date of the relevant surgery for consenting patients will be provided to the histopathology department so that the relevant tissue samples can be identified. The study tissue samples will be extracted from the removed surgical specimens by a pathologist after the routine pathological assessment. These sections will be anonymised and transported to the Institute for Cancer Genetics and Informatics in Oslo for further specialist histological assessment to obtain DNA ploidy of the tumour cells and the tumour: stroma ratio. These samples will be identifiable by their study ID only. Any residual parts of the sections will be returned to Oxford to be held in the cellular pathology department, in line with standard practice for diagnostic surgical specimens.

The DNA Ploidy test is done on monolayers prepared from 50µm sections after microdissecting the tumour area (a video of the laboratory procedure is available at www.youtube.com/watch?v=ERq17Bi3nGI). The stroma measurement is done on standard HE sections (3µm).

8.7. Discontinuation/Withdrawal of Participants from the Study

Each participant has the right to withdraw from the study at any time.

No additional procedures or observations will continue to be required after withdrawal.

Withdrawal from the study will result in the exclusion of the data for that participant from analysis if the patient withdraws their consent to inclusion of their data.

Withdrawn participants will be replaced by further recruitment to the study.

The reason for withdrawal will be recorded in the CRF.

8.8. Definition of End of Study

Receipt of the final analysis from Oslo of the last sample.

9. STATISTICS

An observational study to correlate the results of ploidy and stroma analysis with prognosis in early rectal cancer

IRAS reference: 195159 REC reference: 16/WM/0443

CONFIDENTIAL

Date and version No: 21 October 2016 v1.1

Page 10 of 16

9.1. Description of Statistical Methods

All data will be stored in an Excel worksheet and analysed using Excel and R (a statistical programme).

The DNA ploidy results and tumour: stroma ratio will be correlated with local recurrence and survival. A subgroup analysis will additionally correlate ploidy and stroma with local recurrence and survival with and without adjuvant treatment.

A regression model will be developed incorporating ploidy and tumour: stroma ratio, along with a number of other known prognostic factors that are routinely collected, to assess whether ploidy and stroma have independent prognostic value in determining length of survival free of local recurrence, and length of disease-free survival.

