2. SYNOPSIS

Study Title	An observational study to correlate the results of ploidy and stroma analysis with prognosis in early rectal cancer	
Internal ref. no. (or short title)	Ploidy and stroma in early rectal cancer	
Study Design	Observational study	
Study Participants	Rectal cancer patients	
Planned Sample Size	150 patients	
Follow up duration	Minimum 18 months	
Planned Study Period	2 years	
	Objectives	Outcome Measures
Primary	To compare results of [A] ploidy and [B] stroma analysis with outcome after surgery to remove early rectal cancer	Correlation between [A] ploidy status and [B] tumour: stroma ratio with local recurrence of cancer
Secondary	
To compare results of [A] ploidy and [B] stroma analysis with survival after surgery to remove early rectal cancer
 
To assess predictive value of [A] ploidy and [B] stroma analysis for outcome after surgery to remove early rectal cancer
 
To compare results of [A] ploidy and [B] stroma analysis with outcomes by use of adjuvant treatment
	
Correlation between [A] ploidy and [B] stroma analysis with overall survival after TEM surgery to remove rectal cancer
 
Contribution of [A] ploidy and [B] stroma analysis to a regression model for local recurrence after TEM surgery to remove rectal cancer
 
Subgroup analysis comparing [A] ploidy and [B] stroma results with local recurrence and survival for patients who did and did not receive adjuvant chemo- or radiotherapy

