5. OBJECTIVES AND OUTCOME MEASURES

Objectives	Outcome Measures	Timepoint(s) of evaluation of this outcome measure (if applicable)
Primary Objective To compare results of [A] ploidy and [B] stroma analysis with outcome after surgery to remove early rectal cancer	Correlation between [A] ploidy status and [B] tumour: stroma ratio with local recurrence of cancer	Time between surgery for rectal cancer and local recurrence
Secondary Objectives To compare results of ploidy and stroma analysis with survival after surgery to remove early rectal cancer To assess predictive value of [A] ploidy and [B] stroma analysis for outcome after surgery to remove early rectal cancer To compare results of [A] ploidy and [B] stroma analysis with outcomes by use of adjuvant treatment	Correlation between [A] ploidy and [B] stroma analysis with overall survival after TEM surgery to remove rectal cancer Contribution of [A] ploidy and [B] stroma analysis to a regression model for local recurrence after TEM surgery to remove rectal cancer Subgroup analysis comparing [A] ploidy and [B] stroma results with local recurrence and survival for patients who did and did not receive adjuvant chemo- or radiotherapy	Time between surgery for rectal cancer and death

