6. STUDY DESIGN

An observational study to correlate the results of ploidy and stroma analysis with prognosis in early rectal cancer

IRAS reference: 195159 REC reference: 16/WM/0443

CONFIDENTIAL

Date and version No: 21 October 2016 v1.1

Page 6 of 16

This is an observational study comparing results of two specialised pathology tests with outcome after surgical removal of early rectal cancer. No extra interventions will be carried out on patients.

Over 170 patients have already had an early rectal cancer removed by minimally-invasive surgery (transanal endoscopic microsurgery or TEM) since 2007 in Oxford, and more operations take place each month. Data about the tumour and follow-up on these patients is routinely collected in the Oxford TEM database to ensure that patients receive the appropriate investigations and management after surgery, and that any recurrence of the tumour is promptly detected and treated.

For patients who agree to take part in this study, or who consented to donation of tissue for research at the time of surgery, we will perform the extra pathology tests on the tissue which is stored in the Oxford pathology department as standard practice, and compare the test results with the outcome information contained in the TEM database.

The extra pathology tests will be undertaken in a specialist department in Oslo, Norway. The study will involve sending a small section of the preserved tissue from each consenting patient to Norway for analysis. After analysis, any residual parts of the samples will be returned to the Oxford pathology department.

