9.2. The Number of Participants

The study will recruit 150 participants, including both those who have already had surgery since 2007 and new patients having surgery after the study commences. Similar studies using these techniques of ploidy and stroma analysis compared to outcome after colorectal, breast and ovarian cancer that have produced significant results have generally used between around 150 and 300 patients [ref 3-6]. We expect to be able to recruit 150 patients, from amongst both those who have already had surgery and new patients, within a reasonable time-frame of 18 months.

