9.3. Analysis of Outcome Measures

Data from all participants, excluding any that withdraw consent, will be used in the analysis. The primary outcome measure is the correlation between [A] ploidy status and [B] tumour: stroma ratio with local recurrence of cancer. Secondary outcome measures are i) correlation between [A] ploidy and [B] stroma analysis with overall survival after TEM surgery to remove rectal cancer, ii) the contribution of [A] ploidy and [B] stroma analysis to a regression model for local recurrence after TEM surgery to remove rectal cancer, and iii) Subgroup analysis comparing [A] ploidy and [B] stroma results with local recurrence and survival for patients who did and did not receive adjuvant chemo- or radiotherapy

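### Local recurrence and overall survival are defined as times from surgery but are to be analysed by correlation, with no method for censored times, no censoring rule and no data cut-off

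*Combined protocol and SAP*

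**What the plan says.** - Section 9.1 gives the method for both outcomes: "The DNA ploidy results and tumour: stroma ratio will be correlated with local recurrence and survival". Section 9.3 repeats it for the primary outcome: "The primary outcome measure is the correlation between [A] ploidy status and [B] tumour: stroma ratio with local recurrence of cancer". The first secondary outcome, overall survival, is worded the same way. No coefficient, test or model is named.
- The timepoint column in section 5 reads "Time between surgery for rectal cancer and local recurrence" for the primary outcome and "Time between surgery for rectal cancer and death" for survival.
- Section 9.1 also plans a regression with known prognostic factors for "length of survival free of local recurrence" and for disease-free survival. Section 9.3 lists the regression as secondary outcome ii. Its type is not named, and it does not cover overall survival.
- The synopsis gives follow-up as "Minimum 18 months" and a study period of 2 years. Section 9.2 expects to recruit 150 patients "within a reasonable time-frame of 18 months", from surgery since 2007 and from new operations.
- Section 8.8 ends the study when the last laboratory analysis is received, which is not a follow-up date. Section 9.5 covers missing and spurious data but not censoring.

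**The concern.** A patient operated on in 2007 and one operated on late in recruitment have had very different opportunities to be seen to recur or die. The word correlation leaves two literal readings. One relates the marker to event yes/no, which discards follow-up time and counts anyone who dies early as recurrence-free. The other relates the marker to observed time, which treats a short censored time as if it were a short time to recurrence. Neither handles censoring.

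The choice bears on the primary result of a 150-patient study whose purpose is to judge prognostic value. If it is left until outcomes are linked to marker results, it can be made with the answer in view, and section 9.7 marks the reporting of departures from the statistical plan as not applicable. The follow-up figures also need to agree, because they decide how much information the newest patients can contribute.

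**Working it through.** The plan's 150 cannot be reproduced from a formula: section 9.2 rests it on the size of similar studies and on feasibility, with no event rate, effect size or power.

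**1. Search of the text.** No section names Kaplan-Meier, log-rank, Cox or a competing-risk method. None says when an event-free patient is censored, how death before recurrence is handled, or when data are cut.

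**2. Spread of follow-up.** The protocol date, 21 October 2016, stands in for study start.
- 2007 surgery: 8.8 to 9.8 years by then; adding 2 years gives 10.8 to 11.8.
- Newest patients: 1.5 years at the stated minimum, or 24 − 18 = 6 months if operated on at month 18 and data are cut at month 24.
- Longest to shortest is therefore about 7:1 or about 20:1.

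For scale, with a constant hazard and an assumed 3-year recurrence risk p, the chance that recurrence has occurred by t years is 1 − (1 − p)^(t/3). At p = 20% this is 11% at 1.5 years and 56% at 11 years; at p = 10%, 5% and 32%.

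**3. Do the follow-up figures fit together?** With a cut at month 24, 18 months of follow-up requires surgery by month 24 − 18 = 6. Recruitment runs to month 18, so with even accrual (18 − 6)/18 = two-thirds of new patients fall short. Section 6 says "Over 170 patients have already had an early rectal cancer removed by minimally-invasive surgery" since 2007. 170/9.8 = 17.3 a year, or about 26 in 18 months, so about 17 of 26 fall short.

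**4. Size of the effect (simulation; these inputs are assumptions).** n = 150; 17% new patients (26/150); past surgery uniform over 9.8 years; cut-off 6 months after the last recruit; marker prevalence 40%; 36-month recurrence risk 20% averaged over the cohort; recurrence hazard ratio (HR) 2; 5-year death risk 20%, unrelated to the marker; two-sided 0.05. The falling hazard drops to 1/3 after 3 years and 1/10 after 5. The log-rank test censors at death or cut-off.

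| Analysis of recurrence | Power, falling hazard | Power, constant hazard |
|---|---|---|
| Marker against event yes/no | 46% | 55% |
| Log-rank | 48% | 62-63% |

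- Correlating the marker with observed time, censored times included, gives about 20-24% power in this setting.
- Over 10-20% recurrence risk, 17-25% new patients and a 6- or 18-month minimum, the yes/no loss is 0-9 points.
- With no marker effect, type I error is 4.6-5.3% for both yes/no and log-rank.
- For overall survival (5-year death risk 10-30%), the yes/no loss is 0-6 points at HR 1.5 and 2-12 at HR 2.

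A second simulation, with no competing death and follow-up uniform from 1.5 to 11 years, shows the same ordering. At HR 2 and 10% or 20% three-year risk, power is 54% or 75% (yes/no), 24% or 57% (rank test of observed times) and 56% or 81% (log-rank).

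**The case against.** **The plan already thinks in survival terms.** Section 5 defines times, and the regression in section 9.1 concerns length of survival free of recurrence. On that view correlation is loose wording, and yes/no is the less natural reading. This stands in part: local recurrence is not analysed by correlation alone, and yes/no is one permitted reading rather than a stated choice. But the regression is secondary, its type is unnamed, it omits overall survival, and it does not say whether death ends recurrence-free survival. Reading section 5 literally leads to correlation with observed time, which performs worse.

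**The yes/no loss may be small.** This stands: it can be close to zero.

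**A reader might infer a much larger loss.** If the marker also raises death without recurrence, the simulated yes/no loss reaches 3-20 points at death HR 1.5 and 5-29 at death HR 2. The documents do not establish that effect. Section 4 calls the earlier ploidy effect on survival in rectal cancer small, and says the earlier stroma studies used cancer-related death, which can follow local recurrence.

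**A reader might infer false positives.** These arise if marker results vary with length of follow-up, and nothing in the documents says they do. A marker effect on death has a weaker influence: with death HR 2 and no recurrence effect, yes/no type I error is 4.9-8.5%.

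**A reader might see serious bias from late consent.** Groups B and C must be alive to consent, whereas Group A may include deceased patients (sections 8.1, 8.3, 12.7). With these two groups at 10-49% of past patients and 20% death risk, counting them from surgery overstates 5-year survival by 1.6-8.0 points when the marker does not affect death. The marker HR barely moves (2.02-2.17 against a true 2), and the listed outcomes are marker associations, not absolute survival.

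**Conclusion.** The point holds as a gap in specification that should be closed before outcomes are linked to marker results. For the primary outcome and overall survival as listed, the plan names correlation for what it defines as times, and gives no censoring rule, treatment of death before recurrence or cut-off.

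Under the stated assumptions the cost is 0-9 points of power for recurrence yes/no if the marker does not affect death, and far more for correlation with observed times. Event rates, hazard ratios and marker prevalence are all assumed. So is the 17% share of new patients: proportional recruitment would give 26/(170 + 26) = 13%, with little effect on power.

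The conflict between the follow-up, recruitment and study-period figures is arithmetic on stated numbers. It depends only on cutting data at month 24, and needs reconciling whichever test is used.

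**What to change.** In sections 9.1 and 9.3, replace correlation for these two outcomes with time-to-event analysis from date of surgery: a Cox hazard ratio with 95% confidence interval for each marker, and a log-rank test for marker groups.

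- **Local recurrence:** censor at the last documented recurrence assessment. This matters for Group C, who are no longer followed up in Oxford. Treat death without recurrence as a competing event (cause-specific hazard ratio plus cumulative incidence), and say whether death counts as an event in "length of survival free of local recurrence".
- **Overall survival:** censor at the last date known alive.
- **Cut-off:** state one data cut-off date, and restate the minimum follow-up so that it agrees with 18 months of recruitment and a 2-year study.
- **Late consent:** use delayed entry at consent for Groups B and C as a sensitivity analysis, or as the main approach only if absolute survival curves are reported.

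**Cost.** R is already named. Dates of recurrence, last assessment, and death or last known alive must be extracted for 150 patients, plus consent dates for Groups B and C; section 8.5 promises only outcome information. The work must fit the limit of less than 3 months on investigators' access to personal data in section 10.3. Keeping the 18-month minimum for every patient would put the cut-off at month 18 + 18 = 36, so within the 2-year period the stated minimum may have to become shorter. Delayed entry costs some power: for overall survival at HR 2 and 20% death risk, 60% falls to 59% with Groups B and C at 10% of past patients, and 53% to 46% at 49%.

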4. BACKGROUND AND RATIONALE

Early rectal cancer can be removed by minimally-invasive surgery, and the standard pathological assessment of the removed tumour gives valuable information about how advanced the tumour is. This information is very important in indicating whether the cancer is likely to recur, and therefore in advising the patient after surgery whether further treatment is advisable, and if not, what is the most appropriate follow-up regime. However there is still a lot of uncertainty in these predictions about recurrence of the cancer, and better tests are being sought. This study aims to look at two further pathology tests, ploidy and stroma ratio in the tumour, and compare these test results with outcome in patients who have had an early rectal cancer removed. This will allow us to assess whether these two tests can give greater accuracy in predicting outcome. If so, we would be better able to advise patients with early rectal cancer about their prognosis and further management.

Routine histopathology analysis of a rectal cancer specimen removed at surgery includes assessment of tumour size, depth of invasion, vascular, lymphatic and perineural invasion, tumour involvement of resection margins and nodal involvement. This information is valuable in predicting outcome. For example, predicted rates of local recurrence at 36 months following local excision of rectal cancer by transanal endoscopic microsurgery (TEM) based on tumour size, depth of invasion and lymphatic invasion have been tabulated [1]. However such models are not perfect, and leave room for improvement. Ploidy and stroma ratio are two further tests which have shown some promise in predicting outcome.

Ploidy refers to the number of sets of chromosomes in a cell nucleus. Most human cells are normally diploid, with two sets of 23 chromosomes. Abnormal tumour cells may have a different number of sets of chromosomes, or be aneuploid, having some replicated or deleted chromosomes. In general, aneuploidy in cancer cells is associated with a worse prognosis. An early study of DNA ploidy in rectal cancer using flow cytometry showed an independent but small predictive effect of aneuploidy on survival [2]. Technological advances now allow more accurate and detailed assessment of ploidy. The DNA ploidy status of tumour cells in early ovarian cancer has been found to predict which patients will

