benefit from adjuvant chemotherapy after surgery to remove the ovarian tumour and is used routinely in some centres to aid in decision-making [3].

Stroma ratio refers to the tumour: stroma ratio. A lower proportion of tumour cells or, conversely, a higher percentage of stroma, in a cancer tends to be associated with a poorer prognosis. This ratio has been found to be strongly associated with tumour growth and invasion in colorectal cancers, and to independently predict survival in patients undergoing surgery to remove colorectal tumours [4]. However previous studies have looked mainly at more advanced colon cancers, rather than early rectal cancers, and have used only cancer-related death as the endpoint, rather than looking at local recurrence and response to adjuvant treatments.

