9.4. The Level of Statistical Significance

A 0.05 level of significance will be used.

9.5. Procedure for Accounting for Missing, Unused, and Spurious Data.

All available data will be used. Missing data will not be imputed. Spurious data will be re-checked, and if valid will be included in the analysis.

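### The adjuvant-treatment subgroup analysis gives marker results with and without treatment, but no estimate of whether a marker's effect differs between the two groups

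*Combined protocol and SAP*

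**What the plan says.** The third secondary objective (Synopsis and section 5) is "To compare results of [A] ploidy and [B] stroma analysis with outcomes by use of adjuvant treatment". Section 9.1 gives the method: "A subgroup analysis will additionally correlate ploidy and stroma with local recurrence and survival with and without adjuvant treatment". Section 9.3 restates it as secondary outcome iii, relating marker "results with local recurrence and survival for patients who did and did not receive adjuvant chemo- or radiotherapy". Section 9.4 adds one general rule: "A 0.05 level of significance will be used". Subgroup analyses are not exempted from it.

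The regression model in section 9.1 is meant to show independent prognostic value. Apart from the two markers it names none of its covariates, and it mentions no marker-by-treatment term. Nothing in sections 9.1 to 9.7 describes an interaction, a ratio of hazard ratios or any other comparison of the marker effect between treated and untreated patients.

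Two statements in section 4 bear on how the results will be read. Earlier stroma studies are said to have used cancer-related death as their endpoint, "rather than looking at local recurrence and response to adjuvant treatments". Pathology is described as important for predicting recurrence and "therefore in advising the patient after surgery whether further treatment is advisable". Section 5 measures the primary outcome as "Time between surgery for rectal cancer and local recurrence", and survival also runs from surgery.

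**The concern.** The plan will produce, for each marker and endpoint, one result in patients who had adjuvant treatment and one in those who did not. Given the rationale in section 4, a natural next question is whether the marker matters more in one group than in the other. The plan provides an answer to each half of that question and no estimate of the difference.

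If each result is judged at 0.05, a marker may be significant in one group only. That can happen simply because one group has more events. It could then be reported as a difference in marker effect, or as evidence about response to adjuvant treatment, and influence how the tests are used when further treatment is discussed.

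**Working it through.** **Inputs from the documents.** N = 150 (section 9.2), significance level 0.05 (section 9.4; sidedness not stated, taken as two-sided), follow-up of at least 18 months (Synopsis). There is no power statement, effect size, event count, treated share or marker prevalence, so there is no planned figure to reproduce.

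**Assumed inputs.** A two-level marker with the same true hazard ratio (HR) in both groups; equal outcome risk in treated and untreated patients; D = 15, 22.5 or 30 local recurrences (10%, 15% or 20% of 150); treated share f = 0.2, 0.3 or 0.4; marker prevalence p = 0.3 or 0.5.

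**Step 1: chance that exactly one group is significant.** By the Schoenfeld approximation the expected z-values are

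- treated: ln(HR) × √(D·f·p(1−p))
- untreated: ln(HR) × √(D·(1−f)·p(1−p))

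With group powers a and b, P(exactly one) = a(1−b) + b(1−a).

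*Highest case at HR 2:* D = 30, f = 0.2, p = 0.5, so 6 and 24 events.
- treated: 0.693 × √(6 × 0.25) = 0.849, power 0.136
- untreated: 0.693 × √(24 × 0.25) = 1.698, power 0.397
- P = 0.136 × 0.603 + 0.397 × 0.864 = 0.425

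*Lowest case at HR 2:* D = 15, f = 0.4, p = 0.3, so 6 and 9 events.
- treated: 0.693 × √(6 × 0.21) = 0.778, power 0.122
- untreated: 0.693 × √(9 × 0.21) = 0.953, power 0.159
- P = 0.122 × 0.841 + 0.159 × 0.878 = 0.242

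Over the whole grid, and for overall survival with an assumed 30, 45 or 60 deaths:

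| True HR in both groups | Local recurrence | Overall survival |
|---|---|---|
| 1.5 | 15-22% | 20-34% |
| 2 | 24-42% | 36-59% |
| 3 | 41-62% | 28-62% |

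There is no true difference between groups in any of these cells.

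**Step 2: what a direct contrast would deliver.** The groups do not overlap, so the variances of the two log hazard ratios add: SE(log ratio of HRs) = 1/√(D·p(1−p)·f(1−f)).

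- Best case (D = 30, p = 0.5, f = 0.4): 1/√1.8 = 0.745; 95% CI factor either side exp(1.96 × 0.745) = 4.3.
- Worst case (D = 15, p = 0.3, f = 0.2): 1/√0.504 = 1.409; factor 15.8.
- Power for a ratio of 2: ln 2/SE runs from 0.492 to 0.930, giving 8-15%. For a ratio of 3: 0.780 to 1.474, giving 12-31%.
- For survival the factor is 2.8-7.0.

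**Step 3: simulation of the penalised model.** Settings: n = 150, 3-year horizon, exponential times, equal risk, 1,000 replicates per scenario, Firth fit with Wald intervals. For local recurrence the median CI factor was 4.6-28.2, wider than the approximation. At least one of the four marker-by-treatment cells had no event in 0-56% of studies. The interaction CI wrongly excluded 1 in 0.3-3.7% of studies.

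**Step 4: does later treatment start distort the contrast?** In a large simulation with no true treatment effect or interaction, treatment was assumed to start 2-6 months after surgery. A fixed yes/no grouping gave an adjuvant hazard ratio of 0.74-0.94, but a ratio of hazard ratios of 0.95-1.02. A landmark analysis gave 0.96-1.02 for the ratio, so no gain, and lost about 1-6 of the 15-30 recurrences.

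**The case against.** The strongest reply is that nothing is mismatched. The objective asks for results by use of adjuvant treatment, the outcome measure is a subgroup analysis, and section 9.1 supplies it. Section 4 describes gaps in earlier work and sets no estimand. Its remarks on advising patients concern prognosis. This stands: a reader might infer that the plan fails its own objective, and the wording does not support that.

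Nor does any section propose comparing two p-values. The percentages in Step 1 therefore measure a misreading that the plan leaves open, not an analysis that it declares.

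It is also tempting to say that within-group results can never answer the question. That goes too far: two hazard ratios with standard errors yield the ratio and its CI, as Step 2 shows. Two p-values do not, and section 9 does not commit to reporting hazard ratios or intervals.

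A reader might further infer that counting time from surgery makes a treated/untreated contrast unusable without a landmark or time-dependent model. Step 4 does not bear this out: the distortion falls mainly on the adjuvant main effect.

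Lastly, tumour:stroma is a ratio and no cut-point is given, so figures for a two-level marker may not describe it. That limitation remains.

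**Conclusion.** The plan meets the letter of its objective but specifies no between-group estimate for the question that its rationale invites. Adding one is an inexpensive improvement, not the repair of a contradiction. Without it, a one-sided pattern of significance could be taken for a difference in marker effect. For local recurrence that pattern would arise in roughly 15-62% of studies with no true difference, depending on the common hazard ratio (1.5 to 3). Every input to that range apart from N and the 0.05 level is assumed.

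The contrast itself will be weak. Its value is that a wide interval shows openly that the data cannot separate the groups. Because treatment is not randomised, and section 4 says that pathology informs advice on it, the contrast describes effect modification and cannot show treatment benefit.

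**What to change.** Amend section 9.1, before marker results are linked to outcomes, to state the following.

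- Report subgroup results as hazard ratios with 95% CIs and event counts, and do not compare subgroup p-values.
- For each marker and endpoint, fit one time-to-event model on all patients with marker, adjuvant treatment (yes/no) and their interaction.
- Report the ratio of hazard ratios with its 95% CI as the only basis for any statement that a marker's effect differs by adjuvant treatment.
- Use Firth-penalised likelihood throughout, because marker-by-treatment cells without events are possible. If the treated group has no event, report counts only.
- Label the analysis exploratory and non-causal, and do not interpret the adjuvant main effect, since treatment is not randomised and starts after time zero. No landmark or time-dependent model is required.

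**Cost.** Four small models (two markers by two endpoints). Patients and declared outcome measures do not change. Section 8.5 already has "any (neo-)adjuvant treatment details and outcome information" extracted for Group A, and the other groups' data come from the same database. The amendment goes to the sponsor before the REC (Appendix A) and needs approval if substantial (section 12.3).

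**Downside.** The estimate is imprecise. For local recurrence the CI factor either side is about 4-16 by approximation and about 5-28 in the Firth simulation, with power of about 8-15% for a ratio of 2 and 12-31% for a ratio of 3. The analysis will often leave the question open and cannot show that no difference exists.
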